### **3.6. Description of Treatment Groups**

The intervention will only be administered to those who provide informed consent to participate. Participants will be randomized to receive either oral hydroxychloroquine or placebo along with close monitoring for abnormal glucose tolerance or diabetes. Blood and serum samples for the primary and secondary outcome determinations will be sent to the Core Laboratories for analysis. Clinical laboratory studies may be done at the local sites.

Participants will be randomly assigned in a 2:1 ratio to treatment arms within strata defined by two stratification factors: prior treatment for T1D prevention (prior enrollment in a prevention study and treatment with placebo vs. prior enrollment in a prevention study and treatment with active therapy vs. no prior enrollment in a prevention study) and age group (<8 years old vs. 8 years old or older).

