## 8.2. Primary Analysis

The primary objective of the study is to assess the effect of hydroxychloroquine therapy versus placebo on the risk of progression to Stage 2 or 3 T1D, which is measured from an OGTT or clinically diagnosed with confirmation.

Time to progression to Stage 2 or 3 T1D will be calculated across participants within each treatment group. Time to T1D stage progression will be estimated based on Kaplan-Meier methodology, where participants who were "free of abnormal glucose tolerance and/or T1D" at their last follow-up will be censored at that time point.

This time-to-event outcome will be analyzed using a Cox proportional hazards regression model that stratifies by prior T1D prevention treatment (none vs. placebo vs. active therapy) and age at the time of randomization (<8 yr vs  $\geq$ 8 yr), where treatment effect in this model will be tested using the Wald statistic. Incorporating these as stratification factors in the Cox regression model will allow separate baseline hazard functions to be fitted for each stratum. We will further evaluate differences in event rates in those in the prior treatment stratification factor; specifically, we will assess if there are differential event rates in those enrolling after participation in another prevention trial and ensure that this is accommodated by corresponding stratification in the Cox regression model.

In addition to stratifying on these factors, we will also evaluate if they are effect modifiers on any differences observed in the time to T1D stage progression between these prior treatment groups; i.e., we will formally test for interactions of treatment effect with prior treatment for T1D prevention as well as age on time to T1D stage progression (i.e. progression from Stage 1 to Stages 2 or 3 T1D).

Proportional hazards can be tested to ensure that we can assume that these effects will be parallel. If the assumption of proportional hazard is not appropriate, the data will be examined to determine the cause of non-proportional hazard, such as the presence of a decaying, diverging, or crossing effect of hazard ratios over time. Based on the cause of the non-proportional hazard, post-hoc analyses such as frailty models, parametric models, or models with interactions and time-dependent covariates may be employed.

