### 8.3. Secondary Outcomes and Analyses

A variety of secondary analyses are planned, including the following:

Time to progression to Stage 3 T1D (clinical diabetes) will also be evaluated. Those participants who progress to Stage 2 T1D (abnormal glucose tolerance) prior to developing clinical diabetes will also be included in the time to (Stage 3) T1D analyses. Any participants who develop abnormal glucose tolerance and enroll in another treatment trial or receive other prevention therapy prior to development of Stage 3 T1D will be censored at that time. The treatment arms will be compared in terms of the corresponding distributions of time to progression to Stage 3 T1D (clinical diabetes) using the same methods described for the primary endpoint. Subgroup analyses analogous to those described for time to the composite event definition of progression to Stage 2 **or** 3 T1D will be conducted on the endpoint of time to progression to Stage 3 T1D.

Longitudinal analyses will assess the effects of hydroxychloroquine versus placebo treatment on immunologic and metabolic markers over time up to the onset of progression to Stage 2 or 3 T1D. Differences between groups in the mean levels of quantitative factors over time will be assessed using a normal errors linear model for repeated measures. Differences between groups in the prevalence of qualitative factors over time will be assessed using generalized estimating equations for categorical measures. Generalized estimating equations may also be employed for the analysis of quantitative factors if the assumption of multivariate normal random errors is violated.

Immunologic and metabolic markers will be modeled to determine the effects of hydroxychloroquine versus placebo treatment while adjusting for participant characteristics for each follow-up time point of interest. For continuous endpoints that lend themselves to normal error linear models, ANOVA and ANCOVA models will be employed. Generalized linear modeling will be employed for dichotomous and categorical endpoints by using the most appropriate link functions. Longitudinal analyses may be employed in order to characterize the relationship among the repeated measures during the treatment period and possibly beyond. Due to the exploratory nature of the longitudinal modeling, treatment effect hypothesis testing will not be conducted.

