Criteria for diabetes_onset (T1DM) are based on glucose testing, or the presence of unequivocal hyperglycemia with acute metabolic decompensation (diabetic ketoacidosis). One of the following criteria must be met on two occasions as soon as possible but no less than one day apart for diabetes to be defined: 1. Symptoms of diabetes plus casual plasma glucose concentration ≥ 200 mg/dL (11.1 mmol/L). Casual is defined as any time of day without regard to time since last meal. The classic symptoms of diabetes include polyuria, polydipsia, and unexplained weight loss. 2. Fasting plasma glucose ≥ 126 mg/dL (7 mmol/L). Fasting is defined as no caloric intake for at least 8 hours. 3. 2 hour plasma glucose ≥ 200 mg/dL (11.1 mmol/L). The test should be performed using a glucose load containing the equivalent of 1.75g/kg body weight to a maximum of 75g anhydrous glucose dissolved in water. It is preferred that at least one of the two testing occasions involve an OGTT. Cases identified will be confirmed as having diabetes if the glucose values to make these determinations were obtained in a TrialNet laboratory as part of an OGTT. Cases diagnosed with diabetes by symptoms and casual glucose ≥ 200 mg/dL or by other criteria than the above will be adjudicated by the TrialNet Endpoint Adjudication Committee.

The date of arriving at the study endpoint is the date of the second occasion that meets either of the above criteria or the date in which the participant presented in a state of DKA.

3. Primary Analysis

The study design is a randomized double-blind placebo-controlled trial. The primary objective of the study is to assess the effect of hydroxychloroquine versus placebo on the risk of developing abnormal glucose tolerance (AGT) as measured from an OGTT.

The cumulative incidence of AGT over time since randomization within each treatment group will be estimated from a Kaplan-Meier estimate of the "AGT-free" survival function. Time-to-AGT was discretized to 6-month times in keeping with the OGTT schedule. The difference between groups in the cumulative incidence functions, and the associated hazard functions, will be tested at the 0.05 level, two-sided, using the Cox regression including age as a covariate (1, 5). The critical value for the test statistic, and confidence intervals in this primary analysis will be determined by the group-sequential procedure.

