Longitudinal analyses will assess the effects of hydroxychloroquine versus placebo treatment on immunologic and metabolic markers over time up to the onset of AGT. Differences between groups in the mean levels of quantitative factors over time will be assessed using a normal errors linear model for repeated measures. Differences between groups in the prevalence of qualitative factors over time will be assessed using generalized estimating equations for categorical measures. Generalized estimating equations may also be employed for the analysis of quantitative factors if the assumption of multivariate normal random errors is violated.

4.4 Diabetes.

Additionally, as noted in section 4.9.2 of the protocol, subjects will be able to be followed for the occurrence of diabetes. The treatment arms will be compared on the corresponding

incidence rates of Type 1 diabetes using the log-rank statistic. Subgroup analyses analogous to those described for the AGT endpoint will be conducted on the endpoint of Type 1 diabetes.

Additional, pre-specified secondary analyses are identified as follows:

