1. Evidence that the HR is not constant over the period of follow up will be assessed and the risk of diabetes will be assessed in a PH model. The primary test for treatment effect is based on the Cox model, which assumes a proportional hazard between treatment groups. If there is a true treatment effect but it is not proportional over the follow-up period the test will have substantially less statistical power than stated in the statistical section of the protocol. Therefore, to establish a reasonable guide to pursue the possibility of a non-proportional treatment effect we will use the guideline requiring a significance level of 0.10 or less of the LRT from the standard Cox model. Graphical diagnostics using Schoenfeld residuals will be employed to explore evidence for a monotonically decreasing effect of treatment over the follow-up period. Also, plotting the Kaplan-Meier time-to-AGT rates by treatment group on the log-log scale will provide visual assessment of any diminishing effect of treatment (equal distance separation of curves indicates proportional hazard). We will characterize any such decreasing effect of treatment by model parameterization with monotonically decreasing benefit over the follow-up time. Initially, a treatment interaction with log-transformed time-on-study will be fit to the data and the log likelihood improvement in the fit noted. Other time transforms will be explored only to characterize mathematically the rate of the diminishing effect. Of particular interest will be characterizing the point in follow-up where the hazard ratio is 1. Any variations in proportional hazards other than a monotonically decreasing effect will not be of interest because of the possibility that it is simply random error.

5. Study Power and Sample Size

This study has been designed to provide 83% power to detect a 50% risk reduction in the hazard rate for progression to Stage 2 or 3 T1D (abnormal glucose tolerance or diabetes diagnosis) using a two-sided test at the 0.05 level after a minimum of two years of follow-up on all participants and an expected total study duration (accrual and follow-up) of six years. We note that if accrual is more rapid than expected, minimum follow-up on participants may need to be extended in order to meet the number of events required for the final analysis.

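### SAP 4.4 tests Stage 3 diabetes with a log-rank that names no strata, while Protocol 8.3 calls for the stratified Cox model of the primary analysis; settle on one before unmasking

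*SAP*

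**What the plan says.** Protocol 8.3 compares time to Stage 3 between the arms "using the same methods described for the primary endpoint". Protocol 8.2 gives that method as a "Cox proportional hazards regression model that stratifies by prior T1D prevention treatment (none vs. placebo vs. active therapy) and age" at randomisation, split at 8 years, and adds that "treatment effect in this model will be tested using the Wald statistic".

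SAP 4.4 (Diabetes) instead compares the arms on "incidence rates of Type 1 diabetes using the log-rank statistic". It mentions no strata and no covariates. The first of the additional pre-specified secondary analyses that follow it says that "the risk of diabetes will be assessed in a PH model", again without strata.

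On the design, Protocol 3.6 states: "Participants will be randomly assigned in a 2:1 ratio to treatment arms within strata defined by two stratification factors". These are prior prevention treatment (three levels) and age group (under 8, or 8 and over). Protocol section 8 describes age as an established, significant factor for clinical outcomes in this setting. Protocol 2.1.2 says that younger people move faster through each stage.

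**The concern.** Risk of T1D is the first secondary objective in Protocol 3.2.2, and the two governing documents give it different tests and so potentially different p-values. If this is left open until the data are unmasked, the choice of test can follow the result. That matters whatever the difference in power.

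The SAP's test also appears to set aside both randomisation factors, one of which the protocol itself treats as prognostic. Time to Stage 3 covers both transitions in which age is said to matter. When a stratification factor is strongly prognostic, an analysis that ignores it loses some power, and a hazard ratio from an unstratified model is pulled towards 1.

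**Working it through.** **1. The texts side by side**

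| Item | Protocol | SAP |
|---|---|---|
| Stage 3 comparison | 8.3: primary-endpoint method | 4.4: log-rank, no strata named |
| Primary method | 8.2: Cox stratified by prior treatment and age group, Wald test | 3: Cox with age as a covariate |
| Other model for diabetes | none beyond 8.3 | item 1 after 4.4: PH model, no strata named |
| Basis of the power statement | 8.4: stratified Cox | 5: stratified Cox |

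The SAP names age in section 3 and a stratified model in section 5 when it means them. Silence in 4.4 is therefore most naturally read as an unstratified test.

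**2. The plan's own power figure**

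Inputs from Protocol 8.4: 80 events, hazard ratio (HR) 0.50, 2:1 allocation, two-sided 0.05.

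Power = Φ(√(d·p(1−p))·|ln HR| − z) = Φ(√(80 × 2/9) × 0.693 − 1.960) = Φ(2.923 − 1.960) = Φ(0.963) = 83.2%.

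With the exact split 135/201 it is 82.9%. With 2:1 allocation and the final critical value 1.969 (Protocol 8.5) it is 83.0%. The stated 83% reproduces, but it belongs to the composite endpoint. Neither document gives an event count, rate or power for Stage 3.

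**3. Cost of leaving out the strata, by simulation**

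From the documents: 201 participants, stratified blocked 2:1 randomisation, HR 0.50, 4 years of accrual plus 2 of follow-up, 10% two-year dropout. Assumed: 30% under 8; prior-treatment shares 80/7/13%; Stage 3 placebo rate as shown; exponential times; HR 0.50 within every stratum; equal hazards across prior-treatment levels. Each row is 2,500 trials. The Monte Carlo standard error of one power figure is about √(0.67 × 0.33/2500) = 0.9 points.

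| Placebo Stage 3 rate | Hazard, under 8 vs 8+ | Events | Log-rank power, unstratified | Log-rank power, stratified | Difference (points) | Median HR, unstratified / stratified |
|---|---|---|---|---|---|---|
| 40% at 4 y | 1 | 51 | 69.6% | 68.2% | −1.4 | 0.496 / 0.495 |
| 40% at 4 y | 2 | 50 | 66.5% | 67.0% | +0.5 | 0.505 / 0.499 |
| 40% at 4 y | 3 | 48 | 65.0% | 67.6% | +2.6 | 0.515 / 0.496 |
| 40% at 4 y | 4 | 47 | 59.4% | 64.3% | +4.9 | 0.529 / 0.498 |
| 40% at 2 y | 1 | 86 | 89.1% | 88.0% | −1.1 | 0.502 / 0.501 |
| 40% at 2 y | 2 | 84 | 86.6% | 86.9% | +0.3 | 0.512 / 0.502 |
| 40% at 2 y | 3 | 80 | 79.4% | 83.9% | +4.5 | 0.534 / 0.503 |
| 40% at 2 y | 4 | 77 | 76.4% | 83.7% | +7.3 | 0.549 / 0.504 |

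With 25% under 8 and a 3-fold ratio the gain from stratifying is smaller: 46.1% to 47.3% (placebo rate 25% at 4 years), 64.0% to 66.0% (40% at 4 years) and 80.6% to 83.8% (40% at 2 years).

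**4. Fewer events, two-stage course**

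Yearly hazards from the documents: Stage 1 to 2, −ln(0.60)/2 = 0.255 (Protocol 8.4); Stage 2 to 3, −ln(0.32)/4 = 0.285 (68% at four years, Protocol 2.1.2). HR 0.50 acts on the first transition only. With 35% under 8 (assumed) this gives about 37 Stage 3 events. Over 1,500 trials per setting, Cox Wald power at 2-, 3- and 4-fold was 42%, 39% and 34% unstratified, against 45%, 44% and 42% stratified by age. The differences are 3, 5 and 8 points. The HR was 0.56, 0.58 and 0.61 unstratified, against 0.54, 0.55 and 0.55.

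With all six randomisation cells (4,000 trials, log-rank, 35% under 8, prior-treatment shares 80/7/13%, about 37 events), power unstratified against stratified was:
- ratio 1: 46.7% vs 45.6% (−1.1)
- ratio 1.5: 46.6% vs 46.4% (−0.2)
- ratio 2: 45.5% vs 48.0% (+2.5)
- ratio 3: 43.2% vs 50.8% (+7.6)

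**5. Type I error**

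Under HR 1 (3,000 trials per ratio, 25% under 8), the unstratified log-rank rejected in 4.6%, 5.0% and 3.8% of trials at ratios 1, 2 and 3. There is no inflation.

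**The case against.** Several stronger readings are tempting, and the documents do not support them.

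- **That the log-rank shrinks the treatment effect.** It produces no effect estimate. The drift towards 1 applies only to a hazard ratio from an unstratified model, such as the PH model mentioned after SAP 4.4, and it is modest.
- **That the SAP plans no hazard ratio for diabetes.** The sentence "the risk of diabetes will be assessed in a PH model" implies one. What is missing is the strata and a statement that the hazard ratio and its interval will be reported.
- **That the SAP declares the test unstratified.** It does not use the word. This is inferred from silence, though it is the natural reading.
- **That power is certainly lost.** The documents call age significant but give no size. The only remark on the spread between strata, in Protocol 8.4 and SAP 5, supposes slight variation in the placebo hazards, and it concerns the composite endpoint. With slight variation, stratifying gains nothing, and with none it costs about 1 point. Six cells for some 37 events is also thin, although the six-cell results above show that the penalty is small.

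It is also fair to say that Stage 3 is a secondary endpoint with no stated power, and that the SAP's primary test, "using the Cox regression including age as a covariate", is the more consequential departure from Protocol 8.2. All of these limits stand. None of them removes the conflict between Protocol 8.3 and SAP 4.4, and no other SAP text restores the strata.

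**Conclusion.** The two documents specify different tests for the first-listed secondary objective, and this follows from the text without any assumption. The SAP's version, read naturally, ignores the randomisation factors.

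The statistical cost is conditional. It is about zero, within 2 to 3 points of power, if stratum hazards differ by 2-fold or less. It is roughly 3 to 8 points at 3- to 4-fold, and nearer 1 to 3 points at 3-fold if only a quarter of participants are under 8. An unstratified hazard ratio would move from 0.50 to about 0.53-0.55 at 4-fold. These are results at assumed inputs (share under 8, prior-treatment mix, Stage 3 rates, proportional hazards), not bounds.

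Type I error is not inflated in the runs made, and the 83% for the composite endpoint is untouched. The main reasons to act are the open choice between two tests and the fact that the remedy costs almost nothing.

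**What to change.** In SAP 4.4, replace the log-rank with the Protocol 8.2 Cox model, stratified by the randomisation factors and tested by Wald. Alternatively, keep a log-rank but stratify it by the same factors. Either way, report the stratified hazard ratio with its confidence interval, and use the same strata in the PH model for diabetes listed after 4.4. Spell out the levels: Protocol 3.6 and 8.2 give prior treatment three levels, while Protocol 8.4 and SAP 5 describe it only as whether or not previously treated.

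Reconcile SAP section 3 with Protocol 8.2 in the same amendment, since the Cox model with age as a covariate departs from the stratified model in the same way.

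The cost is a change of SAP wording before unmasking, with no new data, and about 1 point of power on Stage 3 if the strata prove not to be prognostic.

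### SAP 4.4 item 1 makes p ≤ 0.10 on the standard Cox treatment test its guideline for pursuing non-proportional hazards, and confines interest to a decreasing effect; this is circular, narrower than Protocol 8.2, and can hide early-waning, delayed or crossing effects

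*SAP*

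**What the plan says.** SAP section 4.4, item 1 of the additional pre-specified secondary analyses, opens by promising, without any condition, to assess evidence that the hazard ratio is not constant. It then warns: "If there is a true treatment effect but it is not proportional over the follow-up period the test will have substantially less statistical power". The guideline follows as a consequence of that warning: "we will use the guideline requiring a significance level of 0.10 or less of the LRT from the standard Cox model".

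The tools listed are Schoenfeld residuals, log-log Kaplan-Meier plots and a model: "a treatment interaction with log-transformed time-on-study will be fit to the data and the log likelihood improvement in the fit noted". No significance level is given for that interaction. The point in follow-up at which the hazard ratio reaches 1 is singled out as of particular interest. The item ends with a direction limit: "Any variations in proportional hazards other than a monotonically decreasing effect will not be of interest". The reason given is that such variation may be random error.

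Protocol 8.2 treats the matter differently. Proportional hazards can be tested. If the assumption is not appropriate, the data are examined for the cause, "such as the presence of a decaying, diverging, or crossing effect of hazard ratios over time", and post-hoc models may be used. No p-value for the treatment effect has to be reached first.

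SAP section 11 adds a general undertaking to check the assumptions that underlie the planned analyses.

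**The concern.** The screen is the very test that the SAP has just said performs poorly when the effect is non-proportional. If hydroxychloroquine worked for a limited time, worked late, or helped and then harmed, the average hazard ratio would move toward 1. The Cox test would then tend to miss 0.10, and the guideline would advise against looking further. The SAP wants to know when the hazard ratio reaches 1, yet an early fade to 1 is among the patterns most likely to be screened out.

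The direction limit adds a second exclusion. A diverging effect is set aside whatever the treatment p-value. A crossing effect is admitted only if it is read as a declining benefit carried past a hazard ratio of 1, and the SAP does not say whether it may be. The reason offered, random error, applies equally to a decreasing pattern.

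At stake is the reading of a null or weak primary result. The Cox hazard ratio could be reported as the summary of the trial without the follow-up that shows whether one number describes it. The two documents would also point the analyst to different work.

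**Working it through.** **1. Reproduce the planned power.** SAP section 5 states: "This study has been designed to provide 83% power to detect a 50% risk reduction in the hazard rate", with a two-sided 0.05 test, 80 total events and 2:1 allocation. By Schoenfeld's formula, the expected Z is √(80 × 2/3 × 1/3) × ln 2 = √17.78 × 0.693 = 2.92.
- Critical value 1.960: Φ(2.92 − 1.96) = 83.2%.
- Final boundary 1.969 (SAP section 6): 83.0%.

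The plan's 83% is reproduced.

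**2. Chance of meeting the guideline under proportional hazards.** A two-sided 0.10 test has critical value 1.645. Φ(2.92 − 1.645) = 90%. Simulation gives 91% to 92%.

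**3. Simulation inputs.**
- From SAP section 5: 135 vs 66 participants; placebo two-year event rate 40%, so hazard −ln(0.60)/2 = 0.2554 per year; 10% two-year dropout (the stated upper limit), so −ln(0.90)/2 = 0.0527 per year; four years of accrual, taken as uniform; analysis at the 80th event.
- Assumed, because the documents do not give them: the shape of the hazard ratio over time, and a 0.05 level for the interaction test in step 5.
- Simplified: continuous event times, no age covariate, no strata, no interim stopping.
- About 3,000 trials per scenario, so Monte Carlo error is about one percentage point. Repeat runs agreed within about three points.

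**4. Chance that the Cox likelihood-ratio test gives p ≤ 0.10.**

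| True hazard ratio over time | Guideline met |
|---|---|
| 0.5 throughout | about 92% |
| 0.5 for 12 months, then 1 | about 33% |
| 0.5 for 18 months, then 1 | about 50% |
| 0.5 for 24 months, then 1 | about 63% |
| 1 for 12 months, then 0.5 | about 40% |
| 0.5 for 12 months, then 1.5 | about 12% |
| 0.5 for 18 months, then 1.5 | about 23% |

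Stronger or longer early effects pass more often: 52% (0.3 for one year, then 1), 75% (0.3, 0.6, then 1, by year), 89% (0.25, 0.5, 0.75, then 1, by year) and 93% (0.25 for two years, then 1).

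**5. What the guideline costs in detection.** Detection means an interaction p ≤ 0.05 in the waning direction.

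| True hazard ratio over time | No guideline | With guideline |
|---|---|---|
| 0.5 for 1 year, then 1 | 19% | 6% |
| 0.3 for 1 year, then 1 | 48% | 25% |
| 0.5 for 2 years, then 1 | 16% | 10% |
| 0.3, 0.6, then 1, by year | 44% | 34% |
| 0.25, 0.5, 0.75, then 1, by year | 47% | 43% |
| 0.25 for 2 years, then 1 | 57% | 53% |
| 0.5 for 1 year, then 1.5 | 39% | 5% |
| 0.4 for 1 year, then 1.5 | 52% | 7% |
| 0.3 for 2 years, then 1.5 | 62% | 44% |

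Of the departures that the interaction test would otherwise flag, the guideline discards 6% to 66% in the pure-waning shapes and 30% to 87% in the crossing shapes.

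**The case against.** Four points can be made for the SAP.

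*The guideline often passes.* A reader might infer that the rule usually misses waning. The figures do not support that as a general statement. Among the six pure-waning shapes in step 5, five pass the guideline more than half the time (52% to 93%). With no guideline at all, the interaction test finds waning in only 16% to 57% of trials, so many misses come from having 80 events. This stands. The loss is concentrated in effects that fade early or cross.

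*The assumption is still checked.* A reader might infer that a null hazard ratio would be reported with no check. The documents do not say so. The item's first sentence and SAP section 11 are unconditional, the 0.10 level is called a guideline, and Kaplan-Meier curves by arm belong to the primary analysis. This stands too, but it shows that the text is ambiguous: nothing says whether the residual and log-log plots wait for p ≤ 0.10. That choice would be left until the result is known.

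*The protocol does not commit to examining every pattern.* Correct. Protocol 8.2 is permissive and its list is illustrative. The contrast is that it has no treatment p-value condition and does not exclude diverging or crossing effects.

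*Restraint after a null result is sensible.* Small data sets invite over-reading of time-varying effects. That is a reason to label the results supportive. It does not justify deciding whether to look by means of a test known to weaken in the situation of interest.

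**Conclusion.** The point holds as a flaw in a stated secondary-analysis rule. The 0.10 guideline is circular on the SAP's own reasoning, and the direction limit is narrower than Protocol 8.2. Together they can hide early-waning, delayed or crossing effects. The chance of meeting the guideline falls from about 92% under a constant hazard ratio of 0.50 to about 33% when that effect lasts only 12 months, and to about 12% when it reverses to 1.5 at month 12. For a delayed effect the direction limit excludes the pattern even in the roughly 40% of trials that meet the guideline.

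These sizes depend on assumed effect shapes and on the 80-event trigger in SAP section 5. The timing paragraph in SAP section 7 gives a different trigger, 64 to 70 events in the placebo group, and the figures would change under it. The primary test, its alpha and its decision rule are not affected.

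**What to change.** In SAP section 4.4 item 1:
- Delete the 0.10 guideline and the closing sentence that limits interest to a decreasing effect.
- State that the treatment-by-log-time test and scaled Schoenfeld residuals will be reported for the primary model whatever the treatment p-value, and in either direction.
- Describe any decaying, diverging or crossing pattern, in line with Protocol 8.2.
- Label all of this supportive, with the primary test and alpha unchanged, and note that 80 events give limited power to detect a departure.

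A difference in restricted mean event-free time at 24 months, the planned minimum follow-up, could be added as a summary that does not assume proportional hazards. It is optional: with a 12-month delay it would capture only 12 months of benefit.

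The cost is SAP wording and minor programming. The downside is one or two extra supportive outputs that carry no claim.
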